12.2	INSTITUTIONAL REVIEW BOARD.....	12
12.3	INFORMED CONSENT PROCESS	13
12.3.1	Consent/Assent and Other Informational Documents Provided to Participants	13
12.3.2	Consent Procedures and Documentation.....	13
12.4	PARTICIPANT AND DATA CONFIDENTIALITY	13
13	DATA HANDLING AND RECORD KEEPING.....	14
13.1	DATA COLLECTION AND MANAGEMENT RESPONSIBILITIES	14
13.2	STUDY RECORDS RETENTION	15
13.3	PROTOCOL DEVIATIONS	15
13.4	PUBLICATION AND DATA SHARING POLICY	15
14	STUDY FINANCES	15
14.1	FUNDING SOURCE.....	15
14.2	COSTS TO THE PARTICIPANT.....	15
14.3	PARTICIPANT REIMBURSEMENTS OR PAYMENTS	15
15	STUDY ADMINISTRATION	16
15.1	STUDY LEADERSHIP	16
16	CONFLICT OF INTEREST POLICY	16
17	ATTACHMENTS	17

[figure not shown]
List of Abbreviations

AE	Adverse Event/Adverse Experience
CFR	Code of Federal Regulations
CRF	Case Report Form
DCC	Data Coordinating Center
FFR	Federal Financial Report
HIPAA	Health Insurance Portability and Accountability Act
IRB	Institutional Review Board
MOP	Manual of Procedures
N	Number (typically refers to participants)
NIH	National Institutes of Health
NYC H+H	New York City Health + Hospitals
OHRP	Office for Human Research Protections
PI	Principal Investigator
QI	Quality Improvement
SAE	Serious Adverse Event/Serious Adverse Experience
US	United States

Protocol Summary

Title	Examining the Impact of Family Connectors
Short Title	Family Connectors
Brief Summary	This study will examine the impact of Family Connectors amongst 96 family members of adolescents/young adults with first episode psychosis who were discharged from OnTrack.
Objectives	The study objectives are to examine the association between involvement in Family Connectors, a manualized peer-to-peer support and education program for family members of adolescents or young adults with symptoms of first episode psychosis, and feelings of empowerment, self-efficacy and social support. A total of 96 family members will be enrolled in this study, and will be enrolled in either Family Connectors + a packet of community resources or the community resource alone. Outcomes consist of the family member's feelings of self-efficacy, connection to services and supports, caregiving strain, satisfaction, and perceptions of adolescent/young adult functional outcomes at school and work.
Methodology	RCT with data collection and baseline (T1), follow-up (one-month post-baseline, T2) and posttest (six months past T2xx).
Endpoint	The primary endpoint of the study is when data collection is completed for 96 participants.
Study Duration	Approximately 2 years.
Participant Duration	Approximately 9 months from enrollment to completion of posttest data.
Population	96 adults who are (1) English speaking, (2) 18 years of age or older, (3) a family member of an adolescent/young adult with first episode psychosis who was discharged from OnTrack.
Study Sites	The participating site is the NYU Langone School of Medicine and Washington University.
Number of participants	96 family members will be enrolled at NYU Langone School of Medicine
Statistical Analysis	Descriptive analyses will be conducted to calculate means and standard deviations for continuous data and numbers and percentages for dichotomous data. Bivariate and multivariate analyses will examine between and within group differences from baseline to posttest.

Schematic of Study Design

1 Key Roles

[name], [name] Professor of Child and Adolescent Psychiatry
NYU Grossman School of Medicine
[name]
[name]
[contact]
Email: [contact]

[name]
Research Associate
NYU Grossman School of Medicine
[name]
[name]
[contact]
Email: [contact]

[name]
Project Coordinator/Parent Partner
NYU Grossman School of Medicine
[name]
[name]
[contact]
Email: [contact]

[name].
Project Consultant
Clinical Professor
Herbert Wertheim School of Public Health and Longevity Science
University of California, San Diego
[name]
[name]
[contact]
Email: [contact]

[name]
Research Associate
NYU Grossman School of Medicine
[name]
[name]
[contact]
Email: [contact]

[name]
Associate Research Scientist
NYU Grossman School of Medicine
[name]
[name]
[contact]
Email: [contact]

[name]
Project Coordinator
NYU Grossman School of Medicine
[name]
[name]
[contact]
Email: [contact]

2 Introduction, Background Information and Scientific Rationale

2.1 *Background Information and Relevant Literature*

This study will observe the impact of the Family Connectors (FC) model on family members who participated in OnTrack, a treatment program for adolescents/young adults with symptoms of first episode psychosis. The Family Connectors Program is a manualized program that uses a time-limited parent-to parent (i.e. peer parent) support and education program delivered by phone to families of youth with serious mental health difficulties, assisting family members in becoming fully engaged with provider teams who coordinate and provide care. Family Connectors is delivered weekly by phone over the course of between three and six months.

This study has potential for significant impact in five ways: (1) it addresses a high-cost, serious, and significantly debilitating condition (FEP) with the goal of improving client outcomes; (2) it builds on a major national policy initiative and a state-wide priority in NYS; (3) it embeds an intervention tested in prior trials into Coordinated Specialty Care (CSC), enhanced with specialized engagement training offered by Co Lead [name], a prominent mid-career researcher with expertise in engagement of low-income families of color; (4) the model is scalable, as it uses a low-cost, low-intensity enhancement strategy, improving potential for broad scaling in other states; and (5) it is nested within publicly-funded mental health (MH) sites that disproportionately serve low-income Y/YA.

Family Connectors provides emotional support (i.e., reducing parental stress and social isolation through providing emotional support), informational support (i.e., reducing parental stress and social isolation through providing emotional support), informational support (e.g., enhancing parental access to resources and information), positive attitudes (i.e., helping parents develop positive attitudes toward the importance of social support, perceived control, and expected benefits and actions), and caregiver strain.

We are seeking IRB approval to study the impact of Family Connectors upon family member outcomes (e.g., self-efficacy, caregiver strain, satisfaction with the program, social supports), and perceptions of their relative's (adolescents/young adults who participated in OnTrack) function and school outcomes.

2.2 *Rationale*

The study seeks to understand the impact of Family Connectors amongst a sample of family members who participated in OnTrack with their adolescent/young adult family member. Specifically, we seek to examine the impact of FC upon family member outcomes (e.g., self-efficacy, satisfaction with the program, engagement in supports), and functional outcomes and service use amongst adolescents/young adults.

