3.1 Primary Objective

The purpose of this study is to examine the association between involvement in Family Connectors, a manualized peer-to-peer support and education program for family members who participated in OnTrack, a treatment program for adolescents/young adults with first episode psychosis. A total of 96 family members will be enrolled in this study; of them, 48 will be randomly assigned to Family Connectors + a packet of community resources, and 48 will receive the community resource packet alone. Outcomes will consist of caregiver self-efficacy, strain, connection to services, satisfaction with the program, and functioning of the adolescent/young adult at school and work.

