3.2 Secondary Objectives (if applicable)

N/A

4 Study Design and Endpoints

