4.1 Description of Study Design

The study will employ a randomized controlled study design; a total of 96 family members who participated in OnTrack with their adolescent/young adult will be randomized to either Family Connectors or a waitlist comparison group. Data will be collected at baseline (upon the discharge of the adolescent/young adult from OTNY), a follow up (one-month post-baseline) and posttest (seven months post-baseline). For participants in the waitlist condition who choose to work with a Family Connector after their posttest, an identical posttest will be collected at the end of their 6-month intervention period. Both conditions will receive a packet of community resources.

We will conduct a single qualitative interview with each of the Family Connectors to get feedback on their experience as a Family Connector and receive suggestions for further modifications and improvements that can be made to the Family Connectors model.

5 Study Enrollment and Withdrawal

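### The only stated primary endpoint is a data-collection milestone; with no primary outcome or success rule, at least four between-arm comparisons at posttest are unranked

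*Combined protocol and SAP*

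**What the plan says.** The Endpoint row of the Protocol Summary is the only place that states a primary endpoint: "The primary endpoint of the study is when data collection is completed for 96 participants".

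Outcomes appear elsewhere as unranked lists:

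- The Objectives row of the Summary gives "feelings of self-efficacy, connection to services and supports, caregiving strain, satisfaction, and perceptions of adolescent/young adult functional outcomes at school and work". The same row also speaks of empowerment and social support.
- Section 3.1 gives "caregiver self-efficacy, strain, connection to services, satisfaction with the program, and functioning of the adolescent/young adult at school and work". Section 3.2 marks secondary objectives as not applicable, so nothing is placed in a lower tier.
- Section 10.1 has two directional hypotheses. Hypothesis 1 covers self-efficacy, perceived social support and caregiver strain. Hypothesis 2 covers the client's functioning at school and work. Both claim benefit at posttest and at follow-up.

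Section 4 has endpoints in its title, but section 4.1 names none. It sets the assessments as "a follow up (one-month post-baseline) and posttest (seven months post-baseline". Section 10.3 promises bivariate and multivariate analyses without a primary variable, significance level, test order or adjustment. The Statistical Analysis row of the Summary adds only the span: "Bivariate and multivariate analyses will examine between and within group differences from baseline to posttest".

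**The concern.** A primary endpoint should be a variable measured on each participant that the arms can be compared on. Completion of data collection is not one. The protocol also has no fallback: no other section ranks the outcomes, and the sample size is not built on any of them.

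The success rule is open as well. Hypothesis 1 joins its three outcomes with a conjunction. It could be read as requiring all three, or as met by any one. These readings have opposite consequences: the first costs power, the second inflates false positives.

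If neither outcome nor rule is fixed in advance, success could be claimed on whichever T3 comparison looks best. A single positive result could then not be read as confirming the hypotheses. No analysis can repair this after the results are seen, because an outcome chosen at that stage is not pre-specified.

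**Working it through.** **1. Does the sample size reveal an implied primary outcome?** Section 10.2 takes 96 from expected enrolment out of about 150 families a year: 96/150 = 64% uptake. It gives no effect size, standard deviation, significance level or power. The figure cannot be derived from any outcome, so it points to none.

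**2. Which time point carries the randomised comparison?** Section 7.2 places the one-month assessment before the intervention. Section 5.4 gives controls access to a Connector only after T3. T3 is therefore the only randomised comparison made after the intervention.

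**3. How many comparisons at T3?** Hypothesis 1 gives 3. Hypothesis 2 gives 1 if school and work form one measure, or 2 if they are scored separately. The total is 4 or 5. Section 7.1 lists school and work functioning as one domain, which favours 4.

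**4. Error if any one outcome counts as success.** Assumptions, none of them in the protocol: two-sided 0.05 per test (|z| > 1.96), no true effect on any outcome, and one common correlation ρ between test statistics, from 0 to 0.7.

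For ρ = 0:

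- At least one false difference in either direction: 1 − 0.95^k. For k = 4, 1 − 0.8145 = 18.5%. For k = 5, 1 − 0.7738 = 22.6%.
- At least one false claim of benefit: 1 − 0.975^k. For k = 4, 1 − 0.9037 = 9.6%. For k = 5, 1 − 0.8811 = 11.9%.

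For ρ > 0, write each statistic as √ρ·U + √(1−ρ)·E, with U shared and all terms standard normal. The chance of at least one false difference is 1 minus the average over U of [Φ((1.96 − √ρU)/√(1−ρ)) − Φ((−1.96 − √ρU)/√(1−ρ))]^k. For benefit only, drop the second Φ term.

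| Comparisons | ρ | False difference, either direction | False claim of benefit |
|---|---|---|---|
| 1 | – | 5% | 2.5% |
| 4 | 0 | 18.5% | 9.6% |
| 4 | 0.7 | 13.0% | 6.5% |
| 5 | 0 | 22.6% | 11.9% |
| 5 | 0.7 | 14.8% | 7.4% |

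**5. If Hypothesis 1 requires all three outcomes.** A false claim needs a significant result on every outcome, including at least one with no true effect, so the error is at most 5%. The cost is power. If each test alone has 80% power (assumed), all three are significant with probability 0.8³ = 51% at ρ = 0, rising to 66% at ρ = 0.7.

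**6. Do the outcome lists agree?** They do not:

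- Empowerment appears only in the Summary objectives.
- Service use appears as an outcome only in section 2.2.
- Connection to services is in the Summary and section 3.1, but not in section 7.1 or 10.1.
- Social support is in sections 7.1 and 10.1, but not in the list in section 3.1.

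**The case against.** The strongest reply is that this is a modest study with no confirmatory claim. Its aims are worded as examining an association, its size is a feasibility number, and no significance level or decision rule is stated, so there is no error rate to inflate. Part of this stands: the rule that any one outcome suffices is an assumption, and the figures illustrate a risk without describing a stated procedure. It does not remove the defect. The trial is randomised, its hypotheses are directional, and section 5.7.3 lists efficacy and futility as possible grounds for ending the study. Neither ground has a defined meaning without a primary outcome.

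Four stronger readings are tempting, and the documents do not support them:

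- *False success runs at 13% to 23%.* That range counts results in either direction, including ones that favour the control arm. The hypotheses are directional, so the rate of false claims of benefit is about half: 6.5% to 12%.
- *Connection to services adds a sixth comparison.* Section 7.1, which sets out what the questionnaire covers, has no such domain. The Summary's wording, which joins services with supports, may overlap with social support, already counted.
- *Two time points double the count.* Section 10.1 names follow-up as well as posttest, but section 7.2 puts the one-month assessment before the intervention.
- *The Summary's duration proves that posttest is at nine months.* The row reads "Approximately 9 months from enrollment to completion of posttest data", an approximate length of participation. The clear conflict is between section 4.1 (seven months) and section 5.5 (about nine months from baseline to posttest).

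The questionnaire is an attachment that was not available for this review, so the absence of scale names is not a fault. It could change the number of scales, but would be unlikely to rank the outcomes.

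**Conclusion.** The point holds. The stated primary endpoint cannot serve as one, and nothing else in the protocol fills the gap. The count of four comparisons, or five with school and work separate, comes directly from the hypotheses and rests on no assumption about error rates. The percentages do rest on assumptions: two-sided 0.05 per test, a common correlation of 0 to 0.7, and success on any one outcome. Under these the excess is roughly threefold to fivefold, whether counted as false differences (13% to 23% against 5%) or as false claims of benefit (6.5% to 12% against 2.5%). Under the all-three reading there is no inflation, and the price is power. Because the two readings differ so much, the rule has to be written down before any outcome data are examined.

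**What to change.** 1. Settle one outcome list across the Protocol Summary and sections 2.2, 3.1, 7.1 and 10.1. Decide whether empowerment, service use, connection to services and social support are outcomes, and how each is measured.
2. Replace the Endpoint row with one primary outcome chosen by the sponsor. For example: *Primary outcome: family member self-efficacy (scale and score named from the questionnaire attachment) at T3, compared between the randomised arms, two-sided significance level 0.05.* Self-efficacy is only a candidate, taken because Hypothesis 1 lists it first. If the sponsor means Hypothesis 1 to require all three outcomes, state that rule in section 10.1 and refer to it in the Endpoint row.
3. List the remaining outcomes by name as secondary. Either apply Holm's adjustment to that defined family or label them exploratory.
4. Report satisfaction with Family Connectors descriptively among those who received a Connector: the intervention arm at T3, and waitlist participants who later take one at T4. It is not a between-arm test, because controls have had no Connector at T3.
5. State that T3 is the confirmatory time point, and reconcile section 10.1, which also claims benefit at follow-up, with section 7.2.
6. As a separate item, reconcile posttest at seven months in section 4.1 with about nine months in section 5.5. The Methodology row, "posttest (six months past T2xx", also implies seven months (one plus six) and needs its stray characters removed.

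The cost is a protocol amendment, which section 12.2 requires the IRB to approve before it takes effect. No new data or participants are needed. The scientific price is that a positive result on a secondary outcome alone could not be presented as confirmatory.

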2.3 Potential Risks & Benefits

2.3.1 Known Potential Risks

There are no physical, social or economic risks associated with participation. The primary risks associated with this study is (1) a loss of confidentiality and (2) possible discomfort responding. This risk and our actions to protect study participants from the risk are discussed below.

1. To address concerns of breach of confidentiality, all electronic records will be stored on REDCap, a HIPAA-compliant electronic data format platform available through NYU Grossman School of Medicine. All files will be kept confidential to the extent permitted by law. Records will only be available to research staff, and Federal, State and Institutional regulatory personnel (who may view records as part of the routine audits). Privacy will be protected through the use of codes (an ID number) rather than with identifying information so that in the unlikely case that materials are exposed, the subjects' identity is not disclosed. REDCap will be used to administer electronic questionnaires, with no identifying information appearing on the questionnaires. Participants' hard copy contact forms and ID logs will be kept in a locked cabinet on site. Source documents will be shredded in accordance with NYU Grossman Health policy regarding retention of data. All electronic data will be kept on password-protected computers. If results are published, only group information will be reported and they will not contain any identifying information about any individuals.
2. Participants may feel discomfort responding to some of the questions. To mitigate this risk, participants will be notified during consenting that they do not have to answer any questions that make them uncomfortable.

2.3.2 Known Potential Benefits

The benefits of participation in this study include an opportunity to help to determine the impact of Family Connectors as an educational/supportive intervention for family members of individuals with first episode psychosis, which in turn is hypothesized to improve adolescent/young adult functioning in key domains.

3 Objectives and Purpose

3.1 Primary Objective

The purpose of this study is to examine the association between involvement in Family Connectors, a manualized peer-to-peer support and education program for family members who participated in OnTrack, a treatment program for adolescents/young adults with first episode psychosis. A total of 96 family members will be enrolled in this study; of them, 48 will be randomly assigned to Family Connectors + a packet of community resources, and 48 will receive the community resource packet alone. Outcomes will consist of caregiver self-efficacy, strain, connection to services, satisfaction with the program, and functioning of the adolescent/young adult at school and work.

3.2 Secondary Objectives (if applicable)

N/A

4 Study Design and Endpoints

4.1 Description of Study Design

The study will employ a randomized controlled study design; a total of 96 family members who participated in OnTrack with their adolescent/young adult will be randomized to either Family Connectors or a waitlist comparison group. Data will be collected at baseline (upon the discharge of the adolescent/young adult from OTNY), a follow up (one-month post-baseline) and posttest (seven months post-baseline). For participants in the waitlist condition who choose to work with a Family Connector after their posttest, an identical posttest will be collected at the end of their 6-month intervention period. Both conditions will receive a packet of community resources.

We will conduct a single qualitative interview with each of the Family Connectors to get feedback on their experience as a Family Connector and receive suggestions for further modifications and improvements that can be made to the Family Connectors model.

5 Study Enrollment and Withdrawal

5.1 Inclusion Criteria

In order to be eligible to participate in this study, an individual must meet all of the following criteria:

1. English speaking or Spanish speaking,
2. 18 years of age or older,
3. Family member of adolescents/young adults with first episode psychosis who participated in OnTrack.

For the qualitative interviews with our Family Connectors, all individuals working as Family Connectors will be eligible to participate.

For the qualitative interviews with family members, all individuals who worked with a Family Connector, either initially or after their time on the waitlist and posttest, will be eligible to participate.

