5.2 Exclusion Criteria

An individual who meets any of the following criteria will be excluded from participation in this study:

1. Does not provide informed consent.

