10.1 Study Hypotheses

Hypothesis #1: Family members who participate in Family Connectors (i.e., phone-based parent-to-parent support) will demonstrate improved outcomes at post-test and follow-up as measured by higher self-efficacy, greater perceived social support, and lower caregiver strain in comparison to family members who receive the comparison condition.

Hypothesis #2: Identified clients whose family members who participate in Family Connectors (i.e., phone-based parent-to-parent support) will demonstrate improved outcomes at post-test and follow-up as measured by functioning at school and work in comparison to the comparison condition.

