10.2 Sample Size Determination

Our sample size was calculated based upon OnTrackNY's annual enrollment numbers; specifically, there are approximately 150 families who graduate each year from Family Connectors; based upon this number, we anticipate 96 will participate.

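### Two relatives of one OnTrack client can enrol and be randomised to different arms, so that client would count in both arms for Hypothesis 2

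*Combined protocol and SAP*

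**What the plan says.** Eligibility in section 5.1 rests on language, age 18 or over, and being a "Family member of adolescents/young adults with first episode psychosis who participated in OnTrack". Section 5.2 has a single exclusion: "Does not provide informed consent". Having a relative already in the trial is not an exclusion.

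The individual is the unit of randomisation. Section 4.1 states that "a total of 96 family members who participated in OnTrack with their adolescent/young adult will be randomized", and section 3.1 that "48 will be randomly assigned to Family Connectors + a packet of community resources, and 48 will receive the community resource packet alone". Neither section randomises by family or links the assignment of relatives. Section 5.4 recruits family members through OnTrack staff, flyers and a listserv, and does not designate a main caregiver.

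Hypothesis 2 in section 10.1 takes the client as its unit. It concerns "Identified clients whose family members who participate in Family Connectors", with the outcome "as measured by functioning at school and work in comparison to the comparison condition". Under section 7.1 this outcome comes from the family member's questionnaire, so each enrolled relative supplies a separate record on the client.

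Section 10.2 derives the sample from families: "there are approximately 150 families who graduate each year". Section 10.3 plans bivariate and multivariate analyses, with no family term and no rule for two records on one client.

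**The concern.** Three units are in use: the family member is randomised, the client is compared in Hypothesis 2, and the family is counted for the sample size. They coincide only if each client has one enrolled relative, and no rule in the protocol secures that.

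If two relatives of one client land in different arms, two things follow. For Hypothesis 2 the client is both exposed and unexposed, and the same person's functioning enters both arm means. For Hypothesis 1 the control relative may hear the information and support that the other relative receives by phone. That would narrow the gap in self-efficacy, social support and strain. Neither can be fully repaired after randomisation. Dropping split pairs loses participants, and keeping them biases the comparison towards no effect.

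**Working it through.** **Inputs.** From section 3.1: 96 participants, 48 per arm. From section 10.2: about 150 families a year. Not in the documents: the share of participants who would enrol as pairs from one family. I assume 10% to 30% as an illustrative range; every size below scales with it.

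**1. The plan's own figure.** 96/150 = 64%. The plan gives no alpha, power, effect size, standard deviation or dropout, so 96 cannot be rebuilt from a sample-size formula. It is a forecast from a count of families.

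**2. Chance that a pair is split.** With 48:48 allocation that ignores family: 2 × 48 × 48 / (96 × 95) = 48/95 = 0.505.

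**3. Expected number of split clients.** Pairs k = 96 × share / 2; split pairs S = k × 0.505; distinct clients = 96 − k.

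| Assumed share in pairs | k | S | Participants in split pairs (2S/96) | Distinct clients |
|---|---|---|---|---|
| 10% | 4.8 | 2.4 | 5% | about 91 |
| 30% | 14.4 | 7.3 | 15% | about 82 |

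With only 5 pairs, treated as independent, the chance of at least one split client is 1 − (1 − 0.505)^5 = 0.97.

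**4. Effect on Hypothesis 2.** Let δ be the true difference. Let q be the fraction of δ that still shows between the two relatives' reports on a split client. The expected observed difference is δ[1 − (1 − q)S/48]. If both relatives report the same outcome (q = 0), the loss is 2.4/48 = 5% to 7.3/48 = 15%. If the Family Connectors relative reports better functioning than the control relative, q exceeds 0 and the loss is smaller. Random disagreement between the two reports averages out and leaves q at 0.

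**5. Effect on Hypothesis 1.** If a control relative in a split pair gains a fraction c of the benefit, the expected difference is δ(1 − cS/48). The documents give no value for c. The loss runs from zero (c = 0) to the same 5% to 15% (c = 1).

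**6. Effect on standard errors.** Let C be the number of same-arm pairs and ρ the correlation between relatives. Then Var(difference) = (2/48)σ²[1 + ρ(C − S)/48]. Under individual 48:48 allocation the expected C − S is k(47/95 − 48/95) = −k/95. For k = 14.4 this is −0.15, and the bracket is 1 − 0.003ρ. Same-arm pairs raise the variance and split pairs lower it, and on average the two cancel.

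**The case against.** The strongest reply is that the planners had one relative per family in mind. Section 10.2 takes 96 from about 150 families, and section 4.1 describes the pool as relatives who took part in OnTrack with their young person, which is narrower than any adult relative. Both points suggest that pairs may be uncommon. However, one is a recruitment forecast and the other a description. Neither is an enrolment rule, and two parents who both took part in OnTrack would satisfy both.

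Second, the Hypothesis 2 outcome is each relative's perception of the client, as the Protocol Summary and section 2.1 make clear. Two parents may differ, so the 5% to 15% is conditional and not established. This stands. It does not remove the problem, because section 10.1 words the hypothesis in terms of clients.

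Third, the manual of procedures named in section 13.3 and the listed contact and consent forms are not available here, and a one-per-family check could sit there. That cannot be excluded, but an eligibility limit belongs in section 5.1.

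A reader might also infer that paired relatives make the standard errors too small. The plan does not support this: it randomises individuals, and step 6 shows that same-arm and split pairs roughly cancel.

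**Conclusion.** The gap is real. As written, the protocol lets relatives of one client be randomised to different arms, and neither the allocation nor the analysis deals with it. Under the assumed 10% to 30% of participants in pairs, about 2 to 7 clients would be split. Hypothesis 2 would be diluted by about 5% to 15% if both relatives report the same client outcome, and by less if their reports differ in line with their arms. Hypothesis 1 would be biased towards no effect by an amount that depends on how much content passes between relatives.

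The documents do not show that this would happen often, or that control relatives live with Family Connectors recipients. Nor do they support the reading that Hypothesis 2 as a whole lacks a valid comparison: only the split clients are affected. The point is a preventable weakness of uncertain size, worth closing because it is hard to repair once split pairs have been randomised.

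**What to change.** Add to section 5.1 that one family member per OnTrack client may enrol and that, if several are interested, the family names the main caregiver. Add a check of the client ID before randomisation, for example in REDCap. The sample size stays at 96.

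The cost is that second relatives are turned away, about 5 to 14 under the assumed range, and must be replaced from other families. The trial would then need 96 families, or 64% of a year's 150, instead of about 82 to 91 (82/150 = 55% to 91/150 = 61%).

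If the sponsor prefers to keep second relatives, assign all relatives of one client to the same arm, include a family term in the analysis, and use one record per client for Hypothesis 2. The family term would then be needed. With no split pairs, the bracket in step 6 becomes 1 + ρk/48, which is 1 + 0.1ρ for k = 4.8 and 1 + 0.3ρ for k = 14.4. An analysis that ignored family would then understate the standard errors.
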